6.0 Study Procedures

Arms and Interventions Two experimental groups

- 1) APIS[®] biomaterial on the head
- 2) APIS[®] biomaterial on the distal lower extremities

Two control groups

- 1) No intervention, standard SIH wound care on the head
- 2) No intervention, standard SIH wound care on the distal lower extremities

Experimental (40 patients): APIS[®] biomaterial. APIS[®] biomaterial placed on post-operative wound.

- 1) Head (20 patients)
- 2) Distal lower extremities (20 patients)
 - a. Device: APIS[®] biomaterial. This biomaterial was FDA cleared in 2019 for management of full and partial thickness wounds, pressure ulcers, venous stasis ulcers, diabetic ulcers, surface wounds, traumatic wounds, surgical wounds, abrasions, and donor site wounds.
 - b. One layer of APIS[®] will be applied to the post-operative wound covered by petrolatum impregnated gauze, a non-stick Telfa pad, gauze, and Opsite tape.

c. The biomaterial will be reapplied if it is completely absorbed at follow up and the wound depth below the epithelial level.

No intervention (40 patients): No APIS[®] biomaterial on post-operative wound.

- 3) Head (20 patients)
- 4) Distal lower extremities (20 patients)
 - a. Post-operative wound will heal via conventional secondary intention. Application of petrolatum impregnated gauze, a non-stick Telfa pad, gauze, and Opsite tape.

This study may be deemed complete prior to reaching above enrollment numbers if statistical significance is achieved or at the discretion of the research team.

Mohs Surgery – Day 0

Patients eligible for study will be offered opportunity to enroll. After informed consent has been obtained, the patient's clinical history, medical history, social history, medication history, and vital signs will be reviewed and documented. Pre and postoperative photos will be obtained and stored in the Electronic Medical Record and Vanderbilt HIPAA compliant Box.

Patients on day of surgery will be provided with a post-operative wound care instruction sheet (for both control and experimental groups). They will also receive a detailed instruction sheet for uploading post-operative photos to Vanderbilt's HIPAA compliant Box.

Subsequent Post-operative Visits – Post operative Day 14 then every 14 days thereafter until complete re-epithelialization is achieved. Patients enrolled in study will be provided a brief questionnaire to complete at in-person office follow-up visits. Post-operative wounds will be assessed for any complications. Size of wounds in addition to photographs will be obtained until complete re-epithelialization is achieved. Patients will also upload post-operative photos to Vanderbilt's HIPAA compliant Box post-operative day 7 then every 14 days thereafter until complete re-epithelialization is complete.

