Patients will self-report their surgical site/wound pain during in office follow-up visits via a questionnaire. Pain scale will range from 1 (no pain) to 10 (worst pain imaginable).

5. Infection

Post-operative wounds will be assessed for infection at regularly scheduled follow-ups. Any suspected infection (e.g. erythema, purulence, malodor) will be cultured and reported. Antibiotic usage for either prophylaxis peri-operatively or treatment will be recorded.

6. Bleeding

Patients will report any bleeding (yes/no) via questionnaires at regularly scheduled follow-ups. Additionally, if there was post-operative bleeding, was an intervention performed to achieve hemostasis (yes/no) and if yes, what intervention.

7. Ease of Wound Care

Patients will self-report the ease of wound care on a scale of 1 (very easy) to 10 (impossible) via questionnaires at regularly scheduled follow-ups.

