4.0 Inclusion/Exclusion Criteria

Inclusion Criteria:

- 18 years of age or older
- Post-operative wounds following Mohs surgery on the head or distal lower extremities
- Single Mohs post-operative defect
- Post-operative wounds greater than 1cm in width
- Depth of defect at least to subcutaneous tissue
- Patients have the ability to provide their own wound care
- Agreeable to regularly scheduled follow-up visits and transmission of photos via HIPAA compliant Vanderbilt University Medical Center Box
- Patients are able to provide informed consent

Exclusion Criteria:

- Under 18 years of age
- Unable to provide informed consent
- Unable to understand oral and written English
- Post-operative wounds not appropriate for secondary intention healing
- Sensitivity or allergy to APIS[®] biomaterial including collagen and its derivatives, porcine-derived materials or honey
- Immunosuppressed and organ transplant patients
- Post-operative wounds superficial to subcutaneous tissue

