7.0 Risks

Known and expected risks associated with the use of the intervention are the following:

- Allergic reaction to APIS[®] biomaterial
- Surgical site pain, infection, minimal bleeding, oozing, swelling, and/or itching
- Scar
- Loss of confidentiality
- Feeling uncomfortable answering questionnaire

8.0 Reporting of Adverse Events or Unanticipated Problems involving Risk to Participants or Others

Participants will be instructed at the time of consent to contact a member of the study team should they experience any adverse event or unanticipated problem. An on-call

pager number will be provided to study participants. All adverse events and unanticipated problems will be reported to the VUMC IRB in accordance with the VUMC IRB policy. Additionally, all serious adverse events will be reported to the manufacturer of APIS®, SweetBio, Inc (Memphis, TN).

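### The APIS reapplication rule is not reconciled with the complication check, the allergy provisions or the termination clause, so patients who react may drop out of the APIS arm's primary comparison

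*Combined protocol and SAP*

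**What the plan says.** The rule is item c under Arms and Interventions in section 6.0: "The biomaterial will be reapplied if it is completely absorbed at follow up and the wound depth below the epithelial level". It applies to the 40 patients assigned to APIS, 20 with head wounds and 20 with distal lower extremity wounds.

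Five other places bear on the same decision:

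- Section 4.0 excludes patients with "Sensitivity or allergy to APIS[®] biomaterial including collagen and its derivatives, porcine-derived materials or honey".
- Section 6.0, on the post-operative visits from Day 14 and every 14 days after that, says "Post-operative wounds will be assessed for any complications". It gives no consequence for reapplication.
- Section 7.0 lists "Allergic reaction to APIS[®] biomaterial" first among the known and expected risks. Infection is also on that list.
- Section 9.0 allows the investigator to terminate a participant at discretion. The list of grounds is open, and one ground is a significant change in health that makes the participant ineligible. When a participant withdraws voluntarily, the research data are discarded. For participants whom the investigator terminates, section 9.0 does not say what happens to the data.
- Section 10.0 compares mean days to complete re-epithelialization between the groups with a t-test. It does not mention patients who leave before a healing date is observed.

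**The concern.** Reapplication is decided at the visits where complications are assessed, yet the rule names absorption and depth and nothing else. A reader who follows item c alone finds no instruction for a patient who has reacted to the Day 0 layer. A reader who turns to section 9.0 finds only removal from the whole study. No section describes the middle course, in which the device is not reapplied but follow-up continues.

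This matters for the analysis as well as for conduct. Reactions to APIS can arise only where APIS is used. If they lead to termination before healing, the APIS mean is taken over the patients who tolerated the device, while the control mean has no corresponding loss. Section 2.0 lists infection, bleeding and pain as outcomes, but not allergic reaction, device intolerance or number of applications. The first-named device risk would therefore reach the record as an adverse event report and need not appear beside the healing result.

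**Working it through.** The plan has no figure of its own on this point, so there is nothing to reproduce. The check is mainly textual, with some arithmetic for scale.

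**Step 1. Follow one patient.** A patient in the APIS arm has no known sensitivity at entry and satisfies section 4.0. At the Day 14 visit the layer is fully absorbed, the wound is still below the epithelial level, and there is an allergic reaction.

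- Item c: both conditions hold, so it calls for reapplication.
- Complication assessment, same visit: the reaction is noted, with no stated effect on item c.
- Section 4.0: this list governs entry and does not say what follows when sensitivity appears later.
- Section 8.0: the event is reported to the IRB, and to the manufacturer if serious. No action on the device is stated.
- Section 9.0: the investigator may end the patient's participation in the study.

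The written outcomes are reapplication or leaving the study. The second can come before any re-epithelialization date, and section 10.0 has no rule for that patient.

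**Step 2. How likely is it that the case arises?** Input from section 6.0: n = 40 APIS patients. The documents give no reaction rate p, so p is assumed over a range.

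P(at least one reaction) = 1 − (1 − p)^40; expected number = 40p.

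| Assumed p | (1 − p)^40 | P(at least one) | Expected number |
|---|---|---|---|
| 1% | 0.669 | 33.1% | 0.4 |
| 2% | 0.446 | 55.4% | 0.8 |
| 5% | 0.129 | 87.1% | 2 |
| 10% | 0.015 | 98.5% | 4 |

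This is the chance of any reaction. Meeting the unreconciled rule also requires full absorption and an open wound at a visit, so the chance of that is no higher.

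**Step 3. How often is the rule applied?** With visits every 14 days and healing at 42 days (the case-series figure in section 3.0), Days 14 and 28 fall before healing, giving 2 decisions per patient, or 2 × 40 = 80. This is not a maximum, because slower wounds have more visits. The standard healing times quoted in the plan, 57 days for the head and 127 for the leg, would span 4 visits (4 × 14 = 56) and 9 visits (9 × 14 = 126).

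**Step 4. What could the loss do to the mean?** Each lost patient is 1/40 = 2.5% of the arm. Suppose k patients who react are dropped and would have healed D days later than the rest. The mean over the remaining patients is then lower than the mean over all 40 by kD/40. For illustration, let the remaining patients heal at 42 days and those who react heal at the plan's standard times. D is then 57 − 42 = 15 days for the head and 127 − 42 = 85 days for the leg. With k = 2 the shift is 2 × 15/40 = 0.75 days or 2 × 85/40 = 4.25 days. With k = 4 it is 1.5 or 8.5 days. D is an assumption. If patients who react heal no later than the others, there is no shift in APIS's favour.

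**The case against.** Several stronger readings are tempting, and the documents do not support them.

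- **Re-exposure is mandated.** A reader might infer this from the wording of item c. Section 9.0 has an open list of grounds for termination, including loss of eligibility through a change in health, and a new sensitivity to APIS can be read as such a change. The provision is permissive and does not name allergy, but it exists.
- **Item c contradicts the sensitivity exclusion.** Section 4.0 is a set of entry criteria. A rule on who enters and a rule on when to reapply can both stand. What is missing is the link for a sensitivity that appears after entry.
- **The same holds for infection.** Infection is not on the exclusion list. Section 2.0 also provides for it separately: "Any suspected infection (e.g. erythema, purulence, malodor) will be cultured and reported". It shares the missing link between item c and the complication assessment, but not the argument from section 4.0.
- **Reactions vanish from the record.** Section 8.0 sends all adverse events to the IRB. What can be lost is the healing time and a visible count beside the result, not every trace of the event.
- **The trial needs a harm-based stopping rule.** A reader might infer this from "This study may be deemed complete prior to reaching above enrollment numbers if statistical significance is achieved or at the discretion of the research team". Significance is the only named criterion, but the team's discretion can include harm. A numeric harm threshold is a design preference, the documents show no error from its absence, and none is proposed here.

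It can also be said that the handling of terminated patients is a general missing-data question and not a fault of item c. That is partly right. The silence in section 10.0 affects every cause of early termination. Item c adds a cause that can act in one arm only, with no written way to stop the device and keep the patient in follow-up.

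**Conclusion.** The point holds as a gap between sections. Item c rests on absorption and depth alone and is not reconciled with the complication assessment, the named risk of allergic reaction, the entry exclusion or discretionary termination. The consequence for the analysis is a possible loss of patients before a healing date, confined to the APIS arm for reactions to APIS, with no stated handling in the t-test.

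The size is uncertain. The 33% to 99% range rests wholly on assumed reaction rates of 1% to 10% and on full enrolment of 40 APIS patients. It gives the chance that a reaction occurs, not that a patient is re-exposed or lost. The shift in the mean depends further on how many of these patients are terminated and how long they would have taken to heal. The point justifies a short amendment. It does not show that the primary result would be wrong.

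**What to change.** Reconcile item c and the visit text in section 6.0 with sections 4.0, 7.0 and 9.0, so that it is clear how the reapplication decision relates to the complication assessment and to a sensitivity that appears after entry. The investigator sets the clinical criterion.

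Then make three changes for the analysis:

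1. State in sections 6.0 and 9.0 that not reapplying APIS is separate from leaving the study. The patient stays on the 14-day visit schedule until re-epithelialization.
2. State in section 10.0 that such patients are analysed in their assigned arm.
3. Record each non-reapplication with its reason in the study data, and report the number of APIS patients stopped for a reaction next to the healing result.

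The cost is a short amendment and one added data field, with no extra patients and no visits beyond the existing schedule. The as-randomised effect may look slightly less favourable to APIS, because patients who stop the device still count. The fix does not help with patients who leave the study altogether. How they are handled when no healing date exists still has to be stated in section 10.0.

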The novel biomaterial APIS[®] (SweetBio, Inc. Memphis, TN) is an advanced synthesis of gelatin, manuka honey, and hydroxyapatite bioengineered to protect wounds, manage exudate, and maintain a moist environment. It is FDA cleared (FDA number K1827250) for wound management across 9 indications including surgical wounds. It has been used successfully in a small case series of 8 patients for post-operative Mohs surgical wounds on the head and distal lower extremities. Time to complete re-epithelialization was 6 weeks (42 days), suggesting a reduction in healing time compared to standard SIH times for the leg and head of 127 and 57 days, respectively.^{10,11} Use of this novel biomaterial to enhance SIH is hypothesized to reduce healing times when compared to standard SIH wound care. This provides a useful option to aid SIH in sites like the lower legs, where healing can be prolonged due to intrinsic factors (e.g., cardiovascular disease, peripheral vascular disease, diabetes) or extrinsic factors (e.g., increased risk of surgical site infection following dermatologic surgery at sites below the knee).^{10,12}

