2.0 Rationale and Specific Aims

Randomized, comparative studies evaluating augmented SIH compared to conventional SIH in dermatologic surgery are limited. This study aims to evaluate whether use of a novel biomaterial enhances SIH, particularly in shortening time to complete re-epithelialization. Patients undergoing Mohs micrographic surgery amenable to SIH on the head and distal lower extremities will be randomized into one of four groups (standard SIH or biomaterial APIS[®] enhanced SIH on the head or distal lower extremities). Patients will have regularly scheduled follow-up with questionnaires at each visit. We aim to evaluate whether use of this novel biomaterial decreases complete reepithelialization times, reduces infection rates, and improves cosmetic outcomes.

Outcome Measures

Primary:

1. Time to complete re-epithelialization

Patients will be seen in office 14 days post-operative, then every 14 days thereafter until complete re-epithelialization is achieved. Patients will also submit photos via Vanderbilt HIPAA compliant Box at regular follow-up intervals (post-operative day 7 then every 14 days thereafter until complete re-epithelialization is achieved). Time elapsed from surgery date to complete re-epithelialization will be noted in days.

Secondary:

1. Patient and Observer Scar Assessment Scale (POSAS) Patient Scale Score Version 2.0

Patients will complete the POSAS Patient Scale after complete re-epithelialization is achieved. The POSAS Patient Scale is a validated and widely accepted scar assessment tool. The patient scale has six questions assessing scar pain, itch, color, stiffness, thickness, and irregularity rated from 1 (no, not at all/normal skin) to 10 (yes, very much/worst imaginable). Scale from 6-60 with a final seventh question rating patient's overall opinion of scar quality (1-10).

2. Visual Analog Scale (VAS) – Provider Scar Ranking

Digital standardized photographs of scars after complete re-epithelialization is achieved will be assessed by two blinded dermatologists using the VAS. This scale ranges from 0 or normal skin to 10 or worst possible scar taking into account the scar's pigmentation, vascularity, contour, observer comfort, and overall severity. VAS scores of novel biomaterial will be compared to standard SIH.

3. Size of wound

Post-operative wounds will be measured at regularly scheduled follow-ups. The area and volume for each patient's wound will be calculated.

4. Pain score

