5.0 Enrollment/Randomization

Patient enrollment will occur at Vanderbilt University Medical Center One Hundred Oaks Department of Dermatology Mohs Surgical Unit. All patients eligible for study may be considered. Patients with Mohs surgical defects on the head and distal lower extremities amenable and conducive for SIH will be randomized to intervention or control by block randomization. Subjects will be randomized in a 1:1 ratio.

Address of enrollment: Vanderbilt Dermatology One Hundred Oaks [name] [contact]

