10.0 Statistical Considerations

The primary endpoint is time to achieve complete re-epithelialization. The mean number of days required to achieve complete re-epithelialization between control and experimental groups will be analyzed with a Student's T-test. The null hypothesis is that there is no statistically significant difference between control and experimental complete re-epithelialization times. Secondary outcomes of patient and observer cosmetic outcome will be compared similarly.

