12.0 Follow-up and Record Retention

Study duration expected to be 12 months. Study data will be maintained by the research team for a minimum of 7 years and potentially indefinitely. This data will continue to be stored in a password protected database file on the Vanderbilt HIPAA compliant Box, in compliance with Vanderbilt University Medical Center's record retention policies. A limited number of IRB trained, and approved study personnel will have access.

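### Section 6.0 allows the trial to end early on statistical significance with no alpha, look schedule, boundary or named comparison, so if that clause is used the false-positive rate of the primary test cannot be derived from the plan

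*Combined protocol and SAP*

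**What the plan says.** Section 6.0 plans 40 patients per arm, 20 on the head and 20 on the distal lower extremities, and then says the study "may be deemed complete prior to reaching above enrollment numbers if statistical significance is achieved or at the discretion of the research team". That sentence has two limbs, significance and discretion. It names no endpoint, comparison or time for the check.

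Section 10.0 is the whole statistical plan. Its primary analysis reads: "The mean number of days required to achieve complete re-epithelialization between control and experimental groups will be analyzed with a Student's T-test". It adds a no-difference null and says the cosmetic outcomes are compared similarly. It gives no alpha, sidedness, power, interim analysis or multiplicity adjustment, and no other section supplies them.

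Three other places bear on the point:

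- **Randomization.** Section 5.0 says patients "will be randomized to intervention or control by block randomization", in a 1:1 ratio. Section 2.0 says patients "will be randomized into one of four groups". Neither says whether the blocks are formed within anatomical site.
- **Blinding.** The only blinded assessors described are the photo raters in section 2.0, where scar photographs "will be assessed by two blinded dermatologists using the VAS".
- **Data access.** Section 12.0 says of the stored data: "A limited number of IRB trained, and approved study personnel will have access". Like section 11.0, this is a confidentiality measure. It does not keep results by arm from the team that decides when the study is complete.

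**The concern.** Ending a study when significance appears means testing before the planned end and continuing whenever the result is not significant. Each extra test is another chance of a false positive, and an ordinary t-test makes no allowance for that. Correcting for it requires the alpha, the number and timing of looks, and the comparison tested, none of which the plan gives.

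If the trial stopped on this limb, its main p-value would carry no known error rate. No later analysis could restore one, because the look history was never fixed in advance. The t-test is the only analysis planned for the primary endpoint, so the trial's main conclusion would be affected.

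**Working it through.** **Inputs from the documents.** Maximum 40 per arm and 20 per cell (section 6.0); Student's t-test (section 10.0); background healing times, given as "standard SIH times for the leg and head of 127 and 57 days, respectively" (section 1.0).

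**Assumptions, because the documents are silent.** Two-sided 0.05 at each look; the number and spacing of looks; the SD of healing time; normal outcomes; every patient's outcome known at the look.

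**The plan's own figure.** The only stated figure is the enrollment of 80. With no alpha, power, SD or design difference given, it can be neither reproduced nor refuted.

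**Step 1: homogeneous patients.** With n per arm at a look, t = (mean difference) / (s_p × √(2/n)) on 2n − 2 degrees of freedom. The trial stops at the first p < 0.05. Simulated under no difference (200,000 trials, Monte Carlo standard error at most 0.10 points):

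| Looks (patients per arm) | Overall false-positive rate |
|---|---|
| 1 (40) | 5.0% |
| 2 (20, 40) | 8.3% |
| 4 (10, 20, 30, 40) | 12.8% |
| 8 (every 5) | 18.2% |

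Repeat runs gave 8.3% to 8.5%, 12.6% to 12.8% and 18.0% to 18.4% for two, four and eight looks. Alpha itself is unstated. At 0.01 per look, four and eight looks give 2.9% and 4.4%; at 0.10 they give 23.8% and 32.1%.

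**Step 2: two sites, arms balanced by site at every look, one pooled t-test.** The site means differ by 127 − 57 = 70 days, so each lies 35 days from the overall mean. The pooled variance is then about SD² + 35². With balanced arms the site gap cancels from the mean difference, whose true variance depends on SD² alone. The test divides by too large a standard error, and its critical value of 1.99 (78 degrees of freedom) acts like 1.99 × √(SD² + 35²) / SD:

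- SD 35: 1.99 × 49.5 / 35 = 2.81, two-sided tail about 0.5%
- SD 50: 1.99 × 61.0 / 50 = 2.43, about 1.5%
- SD 70: 1.99 × 78.3 / 70 = 2.23, about 2.6%

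Simulation (100,000 trials per setting) confirms the one-look rates to within a few tenths of a point and adds the repeated looks:

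| Looks | SD 35 | SD 50 | SD 70 |
|---|---|---|---|
| 1 | 0.5% | 1.7% | 2.8% |
| 2 | 1.0% | 3.0% | 4.8% |
| 4 | 1.7% | 4.7% | 7.6% |

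Four looks multiply the one-look rate by about 2.7 or more (7.6 / 2.8 = 2.7), but the total passes 5% only at SD 70.

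**Step 3: does the plan select a setting?** No. Section 5.0 mentions blocks without saying they are formed within site. The four groups of section 2.0 and the 20 per cell of section 6.0 are compatible with randomization within site but do not establish it. Nor is it stated whether the comparison that triggers stopping is pooled, is made within one site, or concerns a secondary outcome.

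**The case against.** The strongest reply is that the sentence is permissive. If nobody looks and one test is done at 80 patients, repeated testing adds nothing. That stands, and the point is conditional for that reason.

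A reader might go further in three ways that the documents do not support:

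- **That any use of the sentence is repeated testing.** This is true of the significance limb only. Closing for slow accrual without seeing outcomes by arm involves no extra test. The discretion limb causes the problem only if such results inform the decision, which the plan neither says nor rules out.
- **That the error rate must exceed 5%.** With arms balanced by site, two looks stay below 5% at all three assumed SDs. Part of the rise there uses up the pooled test's initial conservatism. What the documents support is that the rate cannot be derived, not that it is above nominal.
- **That an early positive stop must exaggerate the effect.** This tends to happen when outcomes are fully observed. A real early look at days to healing may, however, have outcomes only for patients already healed, and leaving out slow healers can shrink the difference. The plan does not say how unhealed patients would count, so no direction is asserted here and no rates for such looks are given.

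Two practical objections shape the fix. Infection is both a harm and a stated benefit aim: section 2.0 hopes to reduce infection rates, and "Post-operative wounds will be assessed for infection at regularly scheduled follow-ups". Unrestricted review of infection by arm would therefore reopen the door to benefit looks. Also, section 6.0 follows patients until healed with no maximum, so an analysis timed by the end of the last patient's follow-up has no certain date.

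**Conclusion.** The concern holds for the significance limb as written, and for the discretion limb only when outcome results by arm feed the decision. Used in that way, the plan gives no derivable false-positive rate for its primary test. That conclusion rests on the text alone and needs no assumption.

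The size does need assumptions. At two-sided 0.05 per look with homogeneous, fully observed outcomes, the rate goes from about 5% with one look to 18% with eight. With site balance at every look, four looks give about 1.7% to 7.6% over SDs of 35 to 70 days.

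This must be settled before anyone examines results by arm, because it cannot be repaired afterwards.

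**What to change.** Replace the early-completion sentence in section 6.0 with text such as:

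> Enrollment continues to 80 randomised patients (20 per cell). No comparison by arm of the primary or any secondary outcome for benefit is made before a stated data cut-off for the final analysis. Safety data, including infection and bleeding as adverse events, may be reviewed by arm for harm only, and a difference favouring the biomaterial is not a reason to stop. Early closure is allowed only for safety or feasibility, and feasibility closure is decided without reference to arm-level outcome results.

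In section 10.0, state the two-sided alpha of the primary test and define the cut-off so that one unhealed wound cannot hold up the analysis.

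If an efficacy look is wanted, pre-specify its timing, endpoint, comparison, handling of patients not yet healed, and a group-sequential boundary. Two examples among several, for one look at 20 per arm, are p < 0.001 then 0.05, or p < 0.0052 then 0.048. Each gave about 5% overall in simulation with homogeneous, fully observed outcomes; the rate is lower for a site-balanced pooled test (for the second pair, about 0.5%, 1.6% and 2.8% at SDs of 35, 50 and 70).

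The cost is a short amendment and the loss of the informal early stop for efficacy. The sample size stays at 80.
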